### **9.3 Definition of Populations**

Intent-To-Treat analyses will be performed according to the following definition of the intent to treat population: All individuals who are randomized in the study, which is defined as those individuals who complete informed consent, meet inclusion criteria and do not meet exclusion criteria, complete all baseline assessments, are randomized and receive information about their randomization status.

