Interested patients will be referred to the study by their medical provider or nurse care manager via email or phone. Referring providers or nurse care managers will be able to describe the study to patients and obtain verbal consent to share patient names and contact information directly with the study team for study coordinators to reach out. Patients may also hear about the study through Facebook, Instagram, google ads or bulk mail ads and will have the option to express interest to the study team through a google form created to collect contact information. Since we will be recruiting patients from different primary care sites across the region, a trained Research Coordinator (RC) will conduct 15-30 minute phone screens with each interested patient to assess their eligibility. Patients will verbally consent to the phone screen and will be read a statement of confidentiality (see phone screen script included in the application). This will protect patients from unnecessarily consenting to and enrolling in the study and completing

screening measures if there is an obvious reason for their ineligibility that emerges through the phone screen. Decisions on inclusion/exclusion will be made by the RC with support from the PI, CMC medical director, and MINDFUL-OBOT clinical director. The participant will also be asked to provide emergency contact information (name and phone number) for their buprenorphine prescriber (in the demographics survey), who the study team will reach out to provide more context surrounding emergencies or potentially life-threatening AEs involving the participant. If the participant meets inclusion and exclusion criteria, then the RC will contact the patient and suggest scheduling an online study screening and consent visit via zoom videoconferencing. If the participant is deemed ineligible to participate during this screen, their reason for ineligibility will be documented and all pre-screening data will be removed from the pre-screening database.

[figure not shown]

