### Administration

Participants will be enrolled on a rolling basis in preparation for their randomization to either the live-online M-ROCC or live-online control arm. Initially, randomization will only occur once 24 patients are ready for randomization. Following this initial group, every 4 weeks if at least 24 participants have completed baseline measures and are ready to start a group, they will be randomized using randomly selected block sizes of 4, 6 and 8 with a 1:1 ratio (24 weeks of live online M-ROCC : 24 weeks of live online control group). Next, after randomization, the participant will be informed about their assignment and given a start week for group sessions (either live online control or live online M-ROCC LDM) and will be given information about the group and its structure with a start date scheduled. We will aim to recruit constantly, with a new M-ROCC and control group beginning every 4-5 weeks.

We will aim for participants to begin attending control or LDM groups as soon as possible after randomization, but at least within 4 weeks. The study timeline will start

with week 1 being the first week the participant is assigned to start the study assigned group. Participants will continue to participate in standard care at each site while awaiting randomization and group placement, as well as throughout their enrollment in the study. For both study arms, participants will verify their presence with the group leader or research coordinator who will take attendance each week, which will be transferred to REDCap by the research coordinator after group.

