### **Randomization**

We will randomize participants in a 1:1 ratio of M-ROCC arm to control arm. We will randomize participants in randomly selected blocks of 4, 6, or 8 in a 1:1 ratio.

Randomization will be conducted as follows:

- 1) Participants who complete baseline measures and have a scheduling acceptability form will be entered into the randomization database.
- 2) Upon final review of eligibility, eligible participants will be marked as ready for randomization in the study database, which will alert the data analyst by automated email generated by REDCap.
- 3) The data analyst will randomize participants who are ready using a randomly selected block size (4, 6 or 8) (1:M-ROCC; 1:Control) and will enter the randomization status into the Study Status spreadsheet which the research coordinators will have access to and is kept secure within the CHA G Suite system.
- 4) The research coordinator will call the participant by phone to let them know the date/time that they can start LDM/Control.

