#### 6.2.3 Blinding

See Table 2 for blinding status for study staff. Participants will not be blinded to their assigned study arm (M-ROCC vs. control), nor will the research coordinators, data analyst, or methodologists. The PI will be blinded to assigned study arm when reviewing data quality, adverse events, protocol violations, etc.

Table 2. Blinding Status of Study Staff

Study Role	Blinding Status	Time of unblinding
------------	-----------------	--------------------

PI	Blinded	When all primary outcome data have been collected and when database is locked
Data Analyst ([name], [name], [name])	Not Blinded	Will prepare reports for DSMB with unblinded data, but will not have contact with participants.
Methodologists ([name]/[name])	Not Blinded	Will review reports for DSMB with unblinded data, but will not have contact with participants.
RCs	Not blinded	
Clinical/Medical Directors	Not blinded	
Participants	Not blinded	

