## **8. INTERVENTION DISCONTINUATION**

### Participant Withdrawal/Termination Criteria:

#### *Withdrawal/Termination criteria for Participants:*

Participants may be discontinued from just the study intervention (“Group Discontinuation”) OR both the study intervention and study assessments (“Study Withdrawal”) at any time.

Specific reasons for discontinuing a participant (“Group Discontinuation”) from the group are:

1. Voluntary discontinuation by the participant who is at any time free to discontinue his or her participation in the group, without prejudice to further treatment.
2. Safety reasons as judged by the investigator.
3. Substance use disorder or psychiatric symptoms worsen to a level that requires a higher level of care.
4. Revealing private information about other participants in the groups.

Specific reasons for withdrawing a participant (“Study Withdrawal”) from the entire study are:

1. Voluntary discontinuation by the participant who is at any time free to discontinue his or her participation in the study, without prejudice to further treatment.
2. Safety reasons as judged by the investigator.
3. Incorrect enrollment (i.e., the participant does not meet the required inclusion/exclusion criteria) of the participant.
4. Active severe substance use disorder or level of intoxication during study procedures that precludes ability to conduct assessments.

5. Participants unable to complete baseline assessments.

Participants who discontinue will be asked about the reason(s) for their discontinuation and the presence of any adverse events. If possible, they will be seen and assessed by the Principal Investigator. Serious and Unexpected Adverse events will be followed up.

If participants are terminated from group intervention for any reason (except incorrect enrollment or safety concerns that endanger the study team), then they will still be expected to complete their outcome assessments, unless the participant revokes informed consent and withdraws from study.

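### The intent-to-treat set in Section 9.3 leaves out randomised people who are never told their assignment, so it is a modified ITT set under an ITT label

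*Combined protocol and SAP*

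**What the plan says.** Section 9.3 starts from everyone randomised, then narrows that group by joint conditions. Members must have consented, must "meet inclusion criteria and do not meet exclusion criteria, complete all baseline assessments", and must be people who "are randomized and receive information about their randomization status".

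The order of events is clear. Section 5.1 (Administration) states that "after randomization, the participant will be informed about their assignment". In Section 6.2.2 (Randomization) the data analyst enters the allocation in a status spreadsheet that coordinators can open, and then: "The research coordinator will call the participant by phone to let them know the date/time that they can start LDM/Control". Section 6.2.3 says that participants are not blinded, "nor will the research coordinators, data analyst, or methodologists".

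Section 9.6 gives the primary GEE analysis an intent-to-treat design, with multiple imputation for missing data. Section 9.2 relies on intent-to-treat to argue that the primary outcome is insensitive to dropout after randomisation.

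On eligibility, Section 6.2.2 places the last check before allocation: "Upon final review of eligibility, eligible participants will be marked as ready for randomization in the study database". Section 4.3 assigns the judgement: "Decisions on inclusion/exclusion will be made by the RC with support from the PI, CMC medical director, and MINDFUL-OBOT clinical director". Section 5.4 adds a monthly review of compliance with the entry criteria by the data analyst. Section 8 lists this among the reasons for withdrawal from the whole study, with no time limit: "Incorrect enrollment (i.e., the participant does not meet the required inclusion/exclusion criteria) of the participant". It also exempts such people from the expectation that those removed from group still complete their outcome assessments.

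**The concern.** An intent-to-treat set should be fixed by the act of allocation. Here membership also depends on a later event, and the person who brings that event about can see the arm before calling. If effort to reach people, or success in reaching them, differs by arm, the two analysed groups are no longer the two randomised groups.

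Multiple imputation under Section 9.6 does not help, because people outside the population are not imputed. The statement in Section 9.2 that intent-to-treat protects against dropout does not cover people whom the definition itself removes.

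The eligibility wording raises a second and weaker question. Monthly compliance checks make findings of ineligibility after randomisation foreseeable, and neither Section 8 nor Section 9.3 says whether the people concerned stay in the analysis.

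**Working it through.** **1. The plan's own figure (Section 9.2).** Inputs: 192 randomised, ICC 0.01, average cluster size 24, d = 0.45, two-sided alpha 0.05.

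- Design effect = 1 + (24 − 1) × 0.01 = 1.23.
- Effective N = 192 / 1.23 = 156.1, or 78 per arm.
- Power, normal approximation: 0.45 × √(78/2) = 2.81; 2.81 − 1.96 = 0.85; power 80.2%. The exact t-test gives 79.7%.

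The stated power is reproduced to within rounding. It assumes that all 192 are analysed, so analysing everyone allocated needs no larger sample.

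**2. Who falls outside the set.** Setting Sections 9.3, 5.1 and 6.2.2 side by side, the sequence is consent, eligibility, baseline, randomisation, notification. Only notification comes after allocation. A person allocated but never reached meets every condition except the last, and is excluded.

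**3. Possible size.** The documents give no expected number of such people, so the proportion excluded (f), their outcome (μ) and the restriction to one arm are all assumptions. Assume no true effect, with both full arms at the stated control mean of 4.11, and exclusions from M-ROCC only.

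False difference = (4.11 − f × μ) / (1 − f) − 4.11 = f × (4.11 − μ) / (1 − f).

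With μ = 2 of 6 periods:

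- f = 2% (about 2 of 96): 0.02 × 2.11 / 0.98 = 0.04 periods, which is 8% of the planned 4.67 − 4.11 = 0.56.
- f = 5% (about 5 of 96): 0.05 × 2.11 / 0.95 = 0.11 periods, which is 20% of 0.56.

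The pooled SD is √((1.23² + 1.27²)/2) = 1.25. With 78 effective per arm, the two-sided rejection rate with no true effect is 5.5% at f = 2% and 8.6% at f = 5%, instead of 5%. If the same exclusions fall in the control arm, the sign reverses. If f and μ are equal in both arms, the shifts cancel and there is no bias.

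**4. Loss of precision if exclusions are balanced.** Holding the design effect at 1.23, removing 2% or 5% of all 192 lowers power to 79.5% or 78.2%.

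**5. Eligibility.** In Section 9.3 the entry criteria are listed before randomisation, and Section 6.2.2 puts the final review before it. Section 8 has no time limit and exempts the incorrectly enrolled from outcome assessment, but does not say that data already collected are dropped. The texts allow both readings, so this is an ambiguity and not a stated exclusion.

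**The case against.** The best defence is that the mechanism is weak. Someone who has not yet been told the arm cannot become unreachable because of it. People doing badly may well be harder to reach, but in expectation equally so in both arms, which affects who the result applies to and not the randomised comparison. The plan has one call procedure for both arms, randomises only people who have completed baseline and been marked ready, and holds several contact channels plus three close contacts (Sections 6.2.4 and 9.1). Few people should be lost this way. All of this stands, and it is why the bias is conditional. It does not remove the condition from the definition, and it leaves open differing effort by coordinators who can see the arm.

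Three stronger readings are tempting, and the documents do not support them.

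- A reader might infer that Section 9.3 removes people later judged ineligible, and that unblinded staff decide this. The list order and the pre-randomisation review point the other way. Enrolment is defined as the date of consent (Section 6.2.2), so an incorrect enrolment can be found before allocation. Table 2 lists the principal investigator, who supports eligibility decisions, as blinded until database lock.
- A reader might infer that the randomised comparison is certainly broken, or that the damage could never be traced. Neither follows: allocations are recorded, so exclusions can be counted by arm.
- A reader might infer a much larger effect by supposing that every excluded person is in one arm and has no abstinent period. The documents support neither supposition, and the extreme cases conflict with the planning figures. Eight such people in a control arm of 96 with mean 4.11 leave a total of 96 × 4.11 = 394.56 for the other 88. Spread as evenly as whole counts allow (45.44 fours and 42.56 fives), the variance is (45.44 × 16 + 42.56 × 25)/96 − 4.11² = 1.76. The SD is then at least 1.33, above the stated 1.27. Under Section 9.6, people never contacted would also be imputed and not scored 0.

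**Conclusion.** The definition in Section 9.3 is a modified intent-to-treat set, because it conditions on notification after allocation. That conclusion rests on the text alone. Whether it biases the primary result depends on non-contact differing between arms in number or prognosis, which the documents neither predict nor rule out.

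The range of 0.04 to 0.11 periods is an illustration under the assumptions given with it. It measures the selection, not what the fix would recover: imputed outcomes for people never contacted correct the shift only as far as the imputation model predicts how they would have done. The status of people found ineligible after randomisation is a separate gap in wording. The stated power is not in question.

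**What to change.** - In Section 9.3, define ITT as all participants for whom an allocation was generated, analysed in the arm allocated, regardless of contact, attendance or a later eligibility finding.
- In Section 8, state that incorrect enrolment found after randomisation does not remove a person from the ITT set.
- Report by arm the number never notified and the number found ineligible after randomisation.
- Keep the present definition as a sensitivity set.

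Make the change before outcomes are compared by arm, since a population chosen afterwards would be hard to defend. The cost is a wording change and a few more participants with imputed outcomes. No additional recruitment is needed.

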### **9.4 Interim Analyses and Stopping Rules**

This study will be stopped prior to its completion if: (1) the intervention is associated with adverse effects that call into question the safety of the intervention; (2) any new information becomes available during the trial that necessitates stopping the trial; or (3) other situations occur that might warrant stopping the trial. If the DSMB feels that a safety review to consider stopping the trial is required, then a safety review will be scheduled with the PI, and the IRB and sponsor will be informed. While no formal interim analyses are planned, we do plan to provide regular data monitoring for consistency and to decrease missing values. During these checks, we will monitor the data for unusual patterns that might suggest issues related to safety or adverse effects.

## **9.5 Outcomes**

### **9.5.1 Primary Outcome**

Biochemically-confirmed opioid abstinence, which is defined as the number of two-week periods with a negative oral fluid test [negative for opiate, oxycodone, fentanyl, methadone] AND no self-reported illicit opioid use, based on weekly substance use self-report during the final 12 weeks (weeks 13-24) of the study (6 is the highest possible number of negative oral fluid toxicology screen time periods). Participants will be randomly selected to undergo a live-online supervised oral fluid screen at a rate of once every 2 weeks. Negative toxicology screens have been previously used to assess effectiveness of OUD treatment.

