#### Definition:

In this study we will use the FDA definition of adverse events (AEs): “any untoward medical occurrence that may present itself during treatment or administration with a pharmaceutical product [or group-based treatment intervention], and which may or may not have a causal relationship with the treatment.” Serious adverse events for this trial will be defined as any AE temporally associated with the participants’ involvement in research that meets any of the following criteria:

- Results in death;
- Is life-threatening (i.e., any suicide attempt requiring emergency department or inpatient care will be a SAE, but parasuicidal gestures or self-harm that is not life-threatening or requiring immediate medical care will be an AE, but NOT a SAE; any opioid overdose requiring Naloxone reversal will be a SAE);
- Inpatient hospitalization or prolongation of existing hospitalization (other than admissions for substance use disorder, which will be classified as an AE, but this alone is not sufficient to classify as an SAE since this may be for detoxification or as a beneficial step towards recovery);
- Results in congenital anomaly/birth defect;
- Results in a persistent or significant disability/incapacity or permanent incapacity or substantial disruption to conduct of normal life functions;

- Based upon appropriate medical judgement may jeopardize the participant's health and may require medical or surgical intervention to prevent one of the outcomes listed in this definition.

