**Weekly Survey:** Participants will receive a weekly password protected REDCap survey gathering information about their substance use in the last week, retention, buprenorphine adherence, their level of care (e.g., at a detox residential place, regular outpatient, primary care, etc.), enrollment in medication-assisted treatment, as well as their Buprenorphine and Benzodiazepine (if applicable) dosages. This

survey will be sent via an email link to the secure, encrypted REDCap database. If this is impossible this information will be collected using a CHA-IT approved device. Duration: 4 min

**Pain Catastrophizing Scale (PCS):** The Pain Catastrophizing Scale (PCS) is a 13-item scale designed to facilitate research on the mechanisms by which catastrophizing impacts pain experience. Participants will be asked to indicate the degree to which they experience certain thoughts and feelings when experiencing pain (e.g. “I feel I can’t go on”) on a scale from 0 (“Not at all”) to 4 (“All the time”). Duration: 3 min.

**Substance Craving Scale (SUBCS):** The Substance Craving Scale (SUBCS) is a 6-item scale adapted from the Opioid Craving Scale (OCS). The SUBCS assesses participant craving for Opioids (including fentanyl, heroin, methadone, oxycodone or other opioids) and other substance use (including illicit drugs [e.g., cocaine, methamphetamine, etc.], using unprescribed pills [e.g., Adderall, etc.], using prescribed medication in ways or at doses for which they were not prescribed [e.g., Klonopin, etc.], or drinking alcohol). Duration: 2 min.

*Self-Regulation Battery:*

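### The primary outcome lets a fortnight with a recorded opioid overdose count as abstinent, and lets fortnights after a fatal overdose be imputed as abstinent

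*Combined protocol and SAP*

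**What the plan says.** Section 9.5.1 counts "the number of two-week periods with a negative oral fluid test [negative for opiate, oxycodone, fentanyl, methadone] AND no self-reported illicit opioid use". The self-report half draws on the weekly surveys, the window is weeks 13-24, and the maximum is six. On testing it says: "Participants will be randomly selected to undergo a live-online supervised oral fluid screen at a rate of once every 2 weeks". The Précis, Section 1.1, Section 6.2.5 and Section 9.6 use the same two sources and no others.

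Section 9.6 analyses the outcome by GEE on an intention-to-treat basis and handles missing data by multiple imputation. It makes no exception for death. Section 9.3 keeps every randomized participant in the population.

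Outside the outcome, the trial records other evidence on opioid use. Section 7.3 states that "any opioid overdose requiring Naloxone reversal will be a SAE". Section 7.2.1 lists overdose death among the events to be expected in this population. Section 7.4 collects adverse events in each weekly survey, at the assessment visits and ad hoc. The weekly survey in Section 10.1 also asks about "their level of care (e.g., at a detox residential place, regular outpatient, primary care, etc." None of these records enters the primary outcome, the secondary or exploratory lists in Section 9.5.2, or any sensitivity analysis.

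**The concern.** A fortnight that contains a documented opioid overdose is not a fortnight of opioid abstinence, whatever a test on another day shows. The rule as written can nevertheless score it as one. The same holds after a fatal overdose: the person leaves no further tests or surveys, the fortnights become missing, and the imputation fills them with values learned largely from participants who are alive and being tested.

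In both cases the plan reaches a wrong score by following its own rule, so this is more than a missing detail. At stake are the meaning of the outcome's label and, if such events differ between arms, part of the treatment difference. If the scoring is left open, conflicts between the adverse event log and the outcome data would be settled late, by analysts who are unblinded (Section 6.2.3, Table 2).

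**Working it through.** **1. The plan's own figures.** Inputs from Section 9.2: means 4.67 (SD 1.23) and 4.11 (SD 1.27), 96 randomized per arm, effective 78 per arm, cluster size 24, ICC 0.01, two-sided alpha 0.05.

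- Difference: 4.67 − 4.11 = 0.56 periods.
- Pooled SD: √((1.23² + 1.27²)/2) = 1.250, so d = 0.56/1.250 = 0.448 (stated 0.45).
- Design effect: 1 + (24 − 1) × 0.01 = 1.23, and 192/1.23 = 156.1 (stated 156).
- Power at d = 0.45 with 78 per arm: 80.2% by the normal approximation, 79.7% by the t-test (stated as above 80%).

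The design figures reproduce to within rounding. The point concerns how a period is scored and does not make the power statement wrong. The planned means are for negative tests alone. Below they stand in for the test-plus-self-report outcome, which is an assumption.

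**2. Route one: a recorded, non-fatal overdose.** Three things must coincide in the same fortnight: the overdose is logged, the oral fluid test is negative, and neither weekly survey reports illicit opioid use. The period then scores 1 instead of 0. For one participant in one fortnight:

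- shift in the arm mean = 1/96 = 0.010 periods
- share of the planned effect = 0.0104/0.56 = 1.9%

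If the test or survey is missing in that fortnight, the period goes to imputation, with the logged overdose still ignored.

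**3. Route two: a fatal overdose.** This route needs no misreporting. If imputation draws near the planned means, each missing fortnight is abstinent with probability 4.11/6 = 0.69 to 4.67/6 = 0.78. For a death before week 13 all six fortnights are missing:

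- 4.11/96 = 0.043 periods, and 0.0428/0.56 = 7.6%
- 4.67/96 = 0.049 periods, and 0.0486/0.56 = 8.7%

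If the death falls halfway through the window, three fortnights are missing and the figures halve to about 0.021 to 0.024 periods. Imputation by chained equations need not return the arm mean. The limits for a death before week 13 are no shift (all six imputed non-abstinent) and 6/96 = 0.0625 periods, or 11% of 0.56 (all six imputed abstinent).

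**4. Scale against sampling error.** The planned standard error of the difference is 1.250 × √(2/78) = 0.200. One early death imputed at the planned means is 0.043/0.200 to 0.049/0.200, or about a fifth to a quarter of a standard error. What matters is the net excess in one arm. Equal numbers in both arms largely cancel.

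**5. What cannot be computed.** The documents give no rate of overdose or death, and no split by arm.

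**The case against.** The case on the other side is substantial. Tests are randomly timed and supervised by video, and the self-report covers both weeks of each period. Most adverse event information comes from the same participant, so route one usually requires someone to disclose an overdose while denying opioid use, or staff to learn of it separately. That is right, and it makes route one narrow. It does not close it, and it does not touch route two.

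A reader might go further and infer that periods in detoxification or residential care are also wrongly scored. Section 8 lists, as a reason for leaving the group, "Substance use disorder or psychiatric symptoms worsen to a level that requires a higher level of care", and such participants are still expected to complete outcome assessments. The documents do not support that reading. Section 7.3 treats inpatient stays as SAEs "other than admissions for substance use disorder, which will be classified as an AE", and explains that "this may be for detoxification or as a beneficial step towards recovery". Inclusion criterion 5 admits people using benzodiazepines, cocaine or alcohol, so an admission need not concern opioids. A person in residential care with a negative test and no reported use may simply be abstinent. Nor do the documents show that supervised tests take place during such stays.

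A reader might also put a figure on this: if 5% more of one arm spent 2 of 6 fortnights in such care, 0.05 × 2 = 0.10 periods, 18% of 0.56. That needs an imbalance the documents do not give, with every such fortnight scored abstinent and wrongly so. It should not be relied on.

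A last objection stands in part. Coordinators and group leaders pick up events in group sessions, so capture partly follows attendance, and Section 9.2 forecasts dropout from the intervention of 17-28% with M-ROCC and 21-44% with control. An overdose override could therefore penalise the better-attending arm. This calls for a companion analysis. It is not a reason to score a known overdose as abstinence.

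**Conclusion.** The point holds for overdose and for death after overdose. Followed literally, Sections 9.5.1 and 9.6 can count a fortnight with a recorded naloxone-reversed overdose as abstinent, and can impute fortnights after a fatal overdose as mostly abstinent.

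The size per event is modest: about 2% of the planned difference for one discordant fortnight, and 8-9% for one death before week 13. The second figure assumes 96 per arm, all six periods missing, and imputation at the planned means. The total effect is small if events are rare or balanced.

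A reader might infer that the primary comparison is biased towards a particular arm. The documents give no event rates, so neither frequency nor direction can be stated. The correction is worth making because the score is wrong on its face and the data to put it right are already collected.

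**What to change.** Add to Sections 9.5.1 and 9.6:

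1. A fortnight with a recorded opioid overdose is non-abstinent, whatever the test and the surveys show, and also when either is missing.
2. Fortnights after a fatal opioid overdose are non-abstinent and are not imputed.
3. Events and dates for rules 1 and 2 are adjudicated from the adverse event log by someone masked to arm. The principal investigator already reviews adverse events blinded (Section 6.2.3). The extract should omit details that reveal the group.
4. In one pre-specified sensitivity run of the primary GEE, fortnights with an opioid-related admission, or spent in detoxification or residential care, are scored non-abstinent, with their number reported by arm. They do not alter the primary scoring.
5. Overdose counts are reported by arm, and the primary result is also shown without the override, because capture of overdoses may differ with attendance.

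The cost is a few sentences, a short adjudication and two extra model runs. No new data are needed. The remaining downside is the possible unequal capture, which item 5 makes visible but does not remove.
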